3.3.2 Specific sequencing

7 types of neuroblastoma cell lines: SK-N-SH、SH-SY5Y、SH-EP、IMR-32、NB-19、SK-N-BE、SK-K-AS; Detection of gene transcriptional isomer expression using third-generation

sequencing, divided into NMYC amplification group: IMR-32, NB-19, SK-N-BE and NMYC non amplification group: SK-N-SH, SH-SY5Y, SH-EP, SK-N-AS, and compare the two; SH-SY5Y, SH-EP are differentiated from SK-N-SH, and comparison of three cell lines reveals differentiation related specific transcripts.

i) Sequencing experiment process

The process of full-length transcriptome sequencing experiment includes three steps:

- a.Sample extraction and testing;
- b.Library construction;
- c.On machine sequencing.

Kangsheng Zhenyuan strictly controls every production step of sample testing, database construction, and sequencing to ensure the output of high-quality data.

ii) Sample extraction and testing

After extracting total RNA from tissue samples, we use the following methods for detection.

Only after the detection results meet the requirements can we proceed with library construction:

- a.Nanodrop detection of RNA purity (OD 260/280), concentration, and whether the nucleic acid absorption peak is normal; A single database construction requires a total RNA content of 1 μ g, a concentration of $\geq 200\text{ng}/\mu\text{L}$, and an OD260/280 between 1.8 and 2.2.
- b.Agilent 2100 accurately detects the integrity of RNA, with detection indicators including: RIN value, 28S/18S, baseline elevation, and 5S peak;
- c.Electrophoretic detection of RNA sample bands for dispersion, presence of impurities, or contamination of genomic DNA.

iii) Library construction

After passing the sample testing, the library is constructed, and the main process is as follows:

a.Synthesize full-length cDNA of mRNA using Clonetech SMARTerTM PCR cDNA Synthesis Kit. The 3' end of eukaryotic mRNA has a polyA tail structure. Primers with Oligo dT are used to pair with poly-A as A-T base pairs for reverse synthesis of cDNA, and primers are added at the end of the full-length cDNA synthesized by reverse synthesis. Amplify the full-length cDNA obtained through PCR, purify the product with magnetic beads, and quantify using Qubit 3.0.

b.Purify and amplify the full-length cDNA using magnetic beads, and remove some small fragments of cDNA below 1kb.

c.Perform end repair on full-length cDNA and connect to SMRT dumbbell-shaped connectors.

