d.Digest the unconnected fragments using exonuclease and purify them again using magnetic beads to obtain a sequencing library.

e.After the construction of the library is completed, the quality of the library is tested, and only

after the test results meet the requirements can machine sequencing be carried out.

The detection method is:

- a. Use Qubit 3.0 for accurate quantification;
- b. Use Agilent 2100 to detect the library size, and only after the library size meets expectations can machine sequencing be performed.

iv) On-machine sequencing

After passing the library inspection, use PacBio sequencer to perform full-length transcriptome sequencing according to the target offline data volume.

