3.4 Main and secondary research indicators and statistical analysis

Main and secondary indicators: comparison between genes :IMR-32, NB-19, SK-N-BE and NMYC non-amplified groups:SK-N-SH, SH-SY5Y, SH-EP, and SK-N-AS; SH-SY5Y and SH-EP are derived from SK-N-SH differentiation, and differentiation related specific transcripts can be found by comparing the three cell lines.

Statistical analysis: ① Sample size estimation and grouping method, collecting clinical data of laparoscopic/open neuroblastoma surgery performed at Nantong University Affiliated Hospital from 2024 to 2026. ② Grouping method: Random grouping ③ Research data collection and statistical analysis. Researchers should ensure the accuracy, completeness, and timeliness of the data in the Case Report Form (CRF) and all required reports provided to them. Statistical analysis used survival analysis and repeated measurement methods to analyze the data of the experimental group and control group. t-test was used for quantitative data, chi square test was used for count data, Kaplan Meier method and Cox regression analysis were used for survival analysis, and Stata 26.0 was used for statistical software. P<0.05 was considered statistically significant.

4、Ethic principles

Meet the requirements of the Ethics Committee of Nantong University Affiliated Hospital.

5、Plan and Progress

2024.04.01–2024.08.31 Long segment sequencing of 7 neuroblastomas, collecting neuroblastoma and adjacent control groups;

2024.09.01–2025.11.31 Analyze sequencing data and discover over 100 new splicing fragments; Defective cell lines with successful 2–3 gene new splicing.

2025.12.01–2026.03.31 Organize and analyze data, and write a paper.

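### The three-line comparison in section 3.4 has no stated replication, unit of analysis or suitable test; with one library per line it cannot support a P value

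*Combined protocol and SAP*

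**What the plan says.** Section 3.4 lists only cell-line comparisons as main and secondary indicators. One is amplified against non-amplified lines. The other is the three-line comparison, of which it says "differentiation related specific transcripts can be found by comparing the three cell lines". Section 3.3.2 says the same ("comparison of three cell lines reveals differentiation related specific transcripts"), and section 2.2.4 makes it objective i.

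On replication, section 3.3.2 names "7 types of neuroblastoma cell lines" and sets an RNA requirement per library ("A single database construction requires a total RNA content of 1" μg), but it never says how many cultures or libraries each line contributes. The timetable in section 5 has "Long segment sequencing of 7 neuroblastomas, collecting neuroblastoma and adjacent control groups". Depth is given only as sequencing "according to the target offline data volume", with no figure.

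On analysis, the statistical paragraph of 3.4 gives the rule "t-test was used for quantitative data, chi square test was used for count data". It adds repeated-measures methods, Kaplan-Meier and Cox regression, with significance at P<0.05. These methods are to be used "to analyze the data of the experimental group and control group". The paragraph does not mention cell lines, isoforms or reads.

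**The concern.** The indicators are cell-line contrasts, while the statistical paragraph is written for two groups of patients. Kaplan-Meier and Cox cannot apply to cell lines, and no repeated measurement of a line is described. An analyst looking in 3.4 for a test of the three-line contrast is left with the t-test and chi-square.

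With one library per line, the t-test has no error term for a line-versus-line contrast. Chi-square on read counts would still return a P value, but it takes each read as an independent observation, so counting noise is the only variation it allows for. Separately grown cultures and separately prepared, PCR-amplified libraries can differ by more than that. This is not a small-cell problem: the excess error grows with coverage.

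At stake is what P<0.05 means for objective i. Section 5 goes on to target more than 100 new splice fragments and defective cell lines for 2 to 3 genes, so unreliable calls could misdirect later laboratory work.

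**Working it through.** The plan gives no sample size, power or error rate for this indicator, so there is no figure to reproduce. The check has two parts.

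**1. Degrees of freedom if there is one library per line**

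From the documents: three lines. Assumed: one library each, two-sided 5%.

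- Line versus line: 1 + 1 − 2 = 0 df. No t-test is possible.
- Three-line ANOVA: 3 − 3 = 0 residual df.
- Parent line against its two derived lines, pooled: 1 + 2 − 2 = 1 df. This can be computed, but the critical t is 12.71. The difference must exceed 12.71 × √(1 + 1/2) = 15.6 pooled SDs, so the test is practically useless.

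The amplified versus non-amplified contrast is different. With the line as the unit it has 3 + 4 − 2 = 5 df (critical t 2.57). The present point does not extend to it.

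**2. Chi-square on reads, if the count-data rule were used that way**

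Assumed, none of it in the documents: three libraries of equal depth, no true difference between lines, mean reads per isoform μ of 20 or 100, negative-binomial dispersion φ from 0.01 to 0.1. The corresponding culture-to-culture CV is √φ, or 10% to 32%.

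The true variance of a count is μ + φμ² = μ(1 + φμ), whereas chi-square allows only μ. The statistic is therefore inflated by about D = 1 + φμ. On 2 df the 5% critical value is 5.99, so the false-positive rate is about exp(−5.99 / (2D)).

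| μ | φ | D | False-positive rate |
|---|---|---|---|
| 20 | 0.01 | 1.2 | exp(−2.50) = 0.08 |
| 20 | 0.1 | 3 | exp(−1.00) = 0.37 |
| 100 | 0.01 | 2 | exp(−1.50) = 0.22 |
| 100 | 0.1 | 11 | exp(−0.27) = 0.76 |

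Simulation of gamma-Poisson counts (40,000 runs, libraries of 1,000,000 reads) agrees. At CV 0.2 and μ = 10, 30, 100, 300 and 1000, the formula gives 12%, 26%, 55%, 79% and 93%; the simulation gave 11%, 25%, 54%, 79% and 93%. With CV 0 the simulated rate is about 5%, so the whole excess comes from the between-library variation that is ignored. At 10 reads and CV 0.1 the rate is only 6.4%.

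**3. What replication would restore**

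With an assumed three independent libraries per line, a pairwise t-test has 4 df (critical t 2.78) and a three-line ANOVA has 6 residual df. Simulated type I error on log counts is 4.6% to 5.2% and 4.7% to 5.2% respectively, for μ from 10 to 1000 and CV from 0.1 to 0.4, before any multiplicity correction.

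**The case against.** A reader might infer that the plan has one library per line and prescribes chi-square on reads, so that ordinary culture noise will be declared significant. The documents do not support that.

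- **One library per line is an inference.** The documents count lines, not cultures or libraries. The timetable entry names what is sequenced, not how many libraries are made from each, and it stands beside the collection of tumour and adjacent tissue. It fits one run per line but does not say so. What can be shown is that replication is unspecified.
- **Chi-square is not assigned to reads.** The rule sits in a paragraph on surgical data, random grouping, the case report form, and experimental and control groups. Count data, set against quantitative data, may well mean categorical patient variables. The plan may then simply name no test for this indicator.
- **No P value is attached to the three-line comparison.** It can be read as descriptive discovery.
- **Some t-test can be computed,** namely the pooled 1 v 2 contrast.
- **The error rates rest on assumed depth and CV,** and are small at the low end.

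All of this stands, and it limits the point to a conditional one. It does not remove it. Section 3.4 is headed as the analysis of these indicators, sets a general P<0.05 rule and excludes nothing from it. On either reading the indicator lacks a stated unit of analysis and a suitable test.

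**Conclusion.** The point holds conditionally and should be addressed. What is certain is that no number of independent cultures or libraries per line is stated, nor a unit of analysis, nor a test that fits the three-line indicator.

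What is conditional:

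- If there is one library per line, line-versus-line t-tests and the three-line ANOVA have no residual degrees of freedom.
- If chi-square were run on reads, its error rate would exceed 5% whenever cultures or libraries vary beyond counting noise. The size ranges from slight at low coverage and low CV to several times nominal for well-covered isoforms. The figures of 8% to 37% and 22% to 76% illustrate the mechanism under assumed depth and dispersion. They are not estimates for this study.

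**What to change.** Add to section 3.4, in substance:

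- The t-test and chi-square rules do not apply to sequencing reads.
- The number of independent cultures and libraries per line is stated.
- Contrasts between lines with one library each are descriptive: fold changes or isoform shares, with no P value.
- Any test of cell-line expression takes the independent library, never the read, as the unit, and uses an overdispersed (negative-binomial) count model.

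This costs only wording, and it serves whichever way the present text was meant. The downside is that the three-line comparison can then claim no statistical significance unless replicate libraries exist.

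Replication is optional and is real laboratory work. At three libraries per line it needs 3 × 2 = 6 extra libraries for the three-line contrast, or 7 × 2 = 14 for all seven lines. At the same total read volume, depth per library falls to a third. If P values are then reported across many isoforms, a multiplicity rule is also needed; the plan has none.

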2.2 Research content and design

2.2.1 research contents

- i) Collect 20 clinical neuroblastoma tumor specimens;
- ii) Deep analysis of sequencing data and tumor specific transcripts;

2.2.2 experimental design

- i) 7 types of neuroblastoma cell lines: SK-N-SH、SH-SY5Y、SH-EP、IMR-32、NB-19、SK-N-BE、SK-K-AS; Detection of gene transcriptional isomer expression using Third Generation Sequencing Technology, divided into NMYC amplification group: IMR-32, NB-19, SK-N-BE and NMYC non amplification group: SK-N-SH, SH-SY5Y, SH-EP, SK-N-AS, and compare the two; SH-SY5Y, SH-EP are differentiated from SK-N-SH, and comparison of three cell lines reveals differentiation related specific transcripts.

- ii) Deep sequencing of tissues from 20 clinical neuroblastoma specimens;

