3.2. Sample size calculation and research grouping

Recruitment is mainly conducted in children with neuroblastoma within the past 2 years, excluding cases that are not suitable for enrollment. This study expects recruitment of 20 children with neuroblastoma.

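### Chi-square is the only test named for count data, although the groups are 3 v 4 cell lines and 20 children; a small-count rule with an exact test is needed (minor)

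*Combined protocol and SAP*

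**What the plan says.** Section 3.4 assigns one method to each type of data. For categorical data the whole instruction is "chi square test was used for count data", and the threshold is "P<0.05 was considered statistically significant". The section does not mention an exact test, a continuity correction, a minimum expected count or sidedness.

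The group sizes are given elsewhere.

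- **Cell lines.** Section 2.2.2 has seven lines, "divided into NMYC amplification group: IMR-32, NB-19, SK-N-BE and NMYC non amplification group: SK-N-SH, SH-SY5Y, SH-EP, SK-N-AS, and compare the two". Section 3.3.2 repeats the grouping, and section 3.4 makes this contrast part of the main and secondary indicators: "comparison between genes :IMR-32, NB-19, SK-N-BE and NMYC non-amplified groups:SK-N-SH, SH-SY5Y, SH-EP, and SK-N-AS". That is 3 v 4. Section 3.4 adds a second comparison, within SK-N-SH and its two derived lines, where "differentiation related specific transcripts can be found by comparing the three cell lines".
- **Children.** Section 3.2 states: "This study expects recruitment of 20 children with neuroblastoma". Section 2.2.3 gives the same number. Section 3.4 adds only "Grouping method: Random grouping", with no ratio.
- **Tissue.** Section 5 mentions collecting tumour and adjacent control tissue, without saying how many adjacent samples or whether they are paired within a child.

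**The concern.** The chi-square P value is a large-sample approximation, and the usual working rule asks for expected counts of at least 5. The plan names this test without a condition, in a study whose groups almost never meet the rule. At these sizes the approximate and exact P values can fall on opposite sides of 0.05. The result can also depend on whether the software applies a continuity correction, which the plan leaves open. At stake is whether a difference in a yes/no variable is reported as significant when an exact calculation does not support it or, with the corrected version, whether a real and complete separation can be reported at all.

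**Working it through.** The plan gives no P value, power or calculated sample size on this point, so there is no figure of its own to reproduce. I enumerated the possible 2x2 tables.

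**Inputs.** Groups of 3 and 4 lines (sections 2.2.2, 3.3.2, 3.4); 20 children (sections 2.2.3, 3.2); threshold 0.05 (section 3.4). Assumed: two-sided tests, independent units, a binary variable, and a range of splits for the children.

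**1. Expected counts**

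- An expected count is row total × column total / N. For 3 v 4 with both outcomes present, the largest possible is 4 × 6 / 7 = 3.43, so every count in every table is below 5.
- For 20 children the smallest expected count is r × c / 20, where r and c are the smaller margins (each at most 10). It reaches 5 only if r × c = 100, that is r = c = 10.

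**2. P values for 3 v 4**

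Pearson: X² = N(ad − bc)² / (product of the four margins). Yates: replace |ad − bc| by |ad − bc| − N/2.

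- 3/3 v 1/4 (the mirror 0/3 v 3/4 gives the same values):
  - Pearson: 7 × 9² / (3·4·4·3) = 3.94, P = 0.047.
  - Yates: 7 × 5.5² / 144 = 1.47, P = 0.225.
  - Fisher: of C(7,4) = 35 arrangements, 4 match the observed table and 1 is less likely, so P = 5/35 = 0.143.
- 3/3 v 0/4 (the mirror 0/3 v 4/4 gives the same values):
  - Pearson: 7 × 12² / (3·4·3·4) = 7.0, P = 0.008.
  - Yates: 7 × 8.5² / 144 = 3.51, P = 0.061.
  - Fisher: 1/35 = 0.029.

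Of the 20 possible tables, these four are the only ones with Pearson P<0.05. Fisher agrees on the two complete separations and disagrees on the other two. Under Yates none is significant.

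**3. Size for 3 v 4**

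With a common detection probability p and q = 1 − p, the four rejecting tables have total probability 4p⁴q³ + 4p³q⁴ + p³q⁴ + p⁴q³ = 5p³q³. Fisher keeps only the last two terms, which sum to p³q³.

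- p = 0.5: Pearson 5/64 = 7.8%, Fisher 1/64 = 1.6%.
- p = 0.3: Pearson 5 × 0.21³ = 4.6%.
- p = 0.2: Pearson 5 × 0.16³ = 2.1% (2.05% before rounding).

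**4. Three-line comparison (1 v 2)**

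Complete separation gives X² = 3 × 2² / (1·2·1·2) = 3, P = 0.083. This is the smallest Pearson P available, so no table can be called significant.

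**5. Twenty children (splits assumed)**

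| Split | Pearson-significant tables | Of these, Fisher P ≥ 0.05 | Range of those Fisher P values | Peak Pearson size |
|---|---|---|---|---|
| 10 v 10 | 46 | 12 | 0.057–0.087 | 4.2% |
| 8 v 12 | 48 | 10 | 0.055–0.109 | 5.9% |
| 5 v 15 | 34 | 8 | 0.053–0.109 | 5.2% |
| 4 v 16 | 30 | 10 | 0.061–0.200 | about 8.9% |

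From 5 v 15 to 10 v 10 the peak size does not exceed 5.9%. At 4 v 16, one carrier among the 4 and none among the 16 gives Pearson P = 0.040 and Fisher P = 0.20.

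**The case against.** The strongest reply is that the plan never says the chi-square test will be used on transcripts. It defines no detected/not-detected variable. Sections 2.2.2 and 3.3.2 speak of isoform expression and section 2.2.4 of differential expression, which read most naturally as quantitative and so fall under the t-test. The chi-square sentence itself follows one about experimental and control groups. This stands, and it makes the cell-line result conditional.

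Four stronger readings are tempting, and the documents do not support them.

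- *The main indicator is a presence/absence search on 3 v 4 lines.* In section 3.4 the phrase about specific transcripts belongs to the three-line comparison, where Pearson cannot reach 0.05.
- *Chi-square generally gives false positives at 3 v 4.* The disagreement is one pattern and its mirror, and only for the uncorrected statistic. An isoform truly confined to one group is significant by Fisher's test too. The 7.8% is a worst case.
- *The children's analysis is badly inflated.* That needs a split such as 4 v 16. One could derive it from the roughly 20% MYCN amplification in section 1.1.1, but nothing says the children are compared by MYCN status, and section 3.1.2 excludes distant metastasis. At 10 v 10 the size stays under 5%.
- *Flagged transcripts decide which genes go into the follow-up cell lines.* Section 5 plans work on 2–3 genes but gives no rule tying that choice to P<0.05.

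The reply does not remove the textual point. Chi-square is the only rule for count data, and if it were used solely for clinical counts in the 20 children, the expected-count condition would still fail unless both margins were 10/10.

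**Conclusion.** The concern holds as a minor, conditional point: the named test does not suit the planned group sizes, and the plan has no fallback. If a yes/no variable is tested on the 3 v 4 lines with the uncorrected statistic, two of the four significant tables are not supported by the exact test. With the corrected statistic even complete separation is missed, so an unspecified software option settles the answer. For the children, the effect runs from none on the error rate (10 v 10) to a peak size of about 8.9% (4 v 16), depending on a split the plan does not give.

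These figures assume two-sided tests and independent units. The second assumption is doubtful for the cell lines, because SH-SY5Y and SH-EP derive from SK-N-SH, so three of the four non-amplified lines share an origin.

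**What to change.** In section 3.4, replace the chi-square wording with: *Fisher's exact test is used for categorical data when any expected count is below 5; exact McNemar is used if tumour and adjacent tissue from the same child are compared.* It would help to name, in the same place, any binary variable to be tested and the groups compared.

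The cost is one sentence and no new data. The downside is conservatism: the peak size of Fisher's test is about 1–3% at these group sizes, so some borderline results are lost. A mid-P version is not a dependable way to recover them. Its size equals Fisher's at 3 v 4, and it reaches 5.5% at 8 v 12 and 5.9% at 7 v 13.

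The change does not deal with the shared origin of the SK-N-SH family of lines or with testing many transcripts at 0.05 each. Those need separate treatment.

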2.2.4 Research objectives

- i) Identifying tumor differentiation related specific transcripts through Third Generation Sequencing Technology of cell lines;
- ii) Identify possible differential expression through Deep Sequencing Technology of clinical tissue samples.

3、Specific research methods (including inclusion criteria, sample size calculation, study grouping, intervention and control, specific research process, primary and secondary research indicators, and statistical analysis)

3.1.Inclusion and exclusion criteria

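### The cell-line isoform comparison has no multiplicity rule, and three lines of one origin are counted as separate lines

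*Combined protocol and SAP*

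**What the plan says.** Section 3.4 gives two cell-line comparisons as the main and secondary indicators, without saying which is which. The first sets IMR-32, NB-19 and SK-N-BE (NMYC-amplified) against SK-N-SH, SH-SY5Y, SH-EP and SK-N-AS (non-amplified). The second compares SK-N-SH, SH-SY5Y and SH-EP with one another to find differentiation-related transcripts. Section 3.3.2 will "use PacBio sequencer to perform full-length transcriptome sequencing" and names no candidate isoforms.

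The statistical paragraph of 3.4 starts from "collecting clinical data of laparoscopic/open neuroblastoma surgery" and continues: "Statistical analysis used survival analysis and repeated measurement methods to analyze the data of the experimental group and control group". It names the t-test for quantitative data, the chi-square test, Kaplan-Meier and Cox regression, and ends with "P<0.05 was considered statistically significant". It does not mention isoforms or cell lines. The readable text contains no false discovery rate, adjusted P value or fold-change cut-off.

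On the origin of the lines the plan is open: "SH-SY5Y and SH-EP are derived from SK-N-SH differentiation". Sections 2.2.2 and 3.3.2 say the same. All three lines still stand as separate members of the four-line group. Replicate libraries are not mentioned.

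Section 2.2.4 adds a tissue objective, "Identify possible differential expression through Deep Sequencing Technology of clinical tissue samples", and the timeline in Section 5 mentions "collecting neuroblastoma and adjacent control groups". Neither has its own testing rule.

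**The concern.** There are two separate problems.

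- **Multiplicity.** A transcriptome-wide comparison tests thousands of isoforms. The plan offers only a per-test threshold meant for single variables. Either that threshold is carried over to isoforms, or a headline indicator has no decision rule.
- **Shared origin.** Lines from one parent can be expected to resemble one another. If they are entered as independent, the non-amplified group looks better replicated than it is, and the P values are too small. A correction applied to P values that are already too small does not deliver its nominal error rate.

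Section 2.1 says the study hopes to find new splice forms and treatment targets. A list of supposedly NMYC-related isoforms made up largely of false calls would work against that aim.

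**Working it through.** **Inputs.** From the documents: threshold 0.05, groups of 3 and 4 lines, three of the four with one origin. Not in the documents, so assumed and varied: the number of unchanged isoforms m0, and the correlation ρ among the three related lines. Tests are taken as two-sided, and the remaining lines as unrelated to one another. The plan has no figure of its own to reproduce here; its 20 children come without a calculation and concern the clinical samples.

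**1. False calls at an unadjusted 0.05.** Expected number = 0.05 × m0:
- 10,000 → 500
- 20,000 → 1,000
- 50,000 → 2,500

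**2. Effect of shared origin on one test.** With unit variance, the mean of the four non-amplified lines has variance (4 + 6ρ)/16 = (1 + 1.5ρ)/4. The true variance of the group difference is therefore 1/3 + (1 + 1.5ρ)/4. The pooled variance estimate has expectation (2 + 3 − 1.5ρ)/5 = 1 − 0.3ρ, and the t-test multiplies it by 1/3 + 1/4 = 7/12. The ratio of true to assumed variance is (1 + 4.5ρ/7)/(1 − 0.3ρ). The error rates below come from 1,000,000 simulated null isoforms per setting (normal data, equal variances, nominal 5%).

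| ρ | variance ratio | seven lines, pooled t | seven lines, Welch | three related lines averaged (3 vs 2), pooled t |
|---|---|---|---|---|
| 0 | 1.00 | 0.050 | 0.040 | 0.040 |
| 0.3 | 1.31 | 0.075 | 0.060 | 0.044 |
| 0.5 | 1.55 | 0.096 | 0.075 | 0.047 |
| 0.8 | 1.99 | 0.139 | 0.100 | 0.049 |

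At m0 = 20,000, the pooled test on seven lines gives about 1,500 / 1,900 / 2,800 false calls at ρ = 0.3 / 0.5 / 0.8, against 1,000 nominal.

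**3. Does Benjamini-Hochberg alone repair this?** Simulation of 20,000 isoforms, of which 1,000 (5%) truly differ by 5 SD. Isoform variances are scaled inverse chi-square with 4 df. The test is a moderated t with prior df 4 and the prior variance estimated from the data, at a 5% false discovery rate (FDR).

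| ρ | seven lines: realised FDR | true isoforms found | one unit (3 vs 2): realised FDR | true isoforms found | seven lines, unadjusted P<0.05: realised FDR |
|---|---|---|---|---|---|
| 0 | 0.047 | 963 | 0.027 | 782 | 0.49 |
| 0.3 | 0.10 | 969 | 0.036 | 749 | 0.59 |
| 0.5 | 0.16 | 975 | 0.040 | 735 | 0.65 |
| 0.8 | 0.31 | 982 | 0.045 | 707 | 0.73 |

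With the prior variance fixed at its true value, the seven-line FDR is lower, about 0.09 / 0.13 / 0.22 at ρ = 0.3 / 0.5 / 0.8. The direction is the same.

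**4. Power after the change.** At 3 SD the one-unit analysis finds only about 10 / 8 / 9 of 1,000 true isoforms at ρ = 0.3 / 0.5 / 0.8. Without variance sharing it finds almost none even at 5 SD: about 1 or fewer of 1,000 in simulation.

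**5. Three-line comparison.** With one library per line there are three values and three line means, so 3 − 3 = 0 residual degrees of freedom. No valid P value can be formed.

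**The case against.** The strongest reply is that the harm is conditional. P<0.05 closes a paragraph about surgery data, case report forms and survival, and nothing says isoforms will be tested by P value. A reader might infer that the plan commits to calling every isoform at P<0.05; the documents do not support that. The gap remains, because no other rule is given for this indicator.

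A second reply is that the work is exploratory. Section 2.2.4 speaks of possible differential expression, and the timeline has an item that begins "Defective cell lines with successful" and appears to mean follow-up of 2-3 genes in altered lines. That can test those genes, but it does not control error in the reported list. Cataloguing new isoforms need not rest on P values, so this point is limited to the group comparison. For the same reason, nothing supports the inference that the target of more than 100 new splicing fragments would be met by chance: the plan does not say they are selected by P value.

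Third, repeated-measurement methods are named and might be thought to cover the related lines. The text ties them to an experimental and a control group, not to cell lines.

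Fourth, absence can be claimed only for the readable text. The technology roadmap under 3.3.1 did not survive extraction and could show replicates.

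Finally, averaging to 3 vs 2 is one of several defensible choices. It merges lines selected because they may differ in differentiation, and it costs power; modelling origin as a correlated block is an alternative. That stands, so averaging is offered below as an example.

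**Conclusion.** The concern holds in this form: a transcriptome-wide group comparison listed among the main and secondary indicators has no multiplicity rule, the only threshold available to it is P<0.05, and three lines of stated common origin are entered as separate lines. It should be fixed.

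The false-call count in step 1 needs only m0 and the condition that P<0.05 is applied to isoforms. The inflation in step 2 also depends on ρ and on the test used; Welch is affected less than the pooled t. The FDR figures in step 3 further depend on the assumed effect size, the share of true effects and the way the prior variance is set. They show direction and rough size and do not predict this study's result.

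Two stronger readings go too far. The plan does not hide the relatedness; it states it and then does not allow for it. Nor does a 3 vs 2 analysis under Benjamini-Hochberg always need the single-call bound of 0.05/20,000 (|t| about 96 on 3 df). The procedure is step-up: with 750 calls the cut-off is 750 × 0.05/20,000 = 0.0019, or |t| about 10.4. Variance sharing is needed because, without it, almost nothing was found in the simulation.

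**What to change.** Add to Section 3.4, in words such as:

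> Isoform group comparisons are called at a Benjamini-Hochberg false discovery rate below 5%, using a moderated test that shares variance across isoforms. The NMYC contrast allows for the common origin of SK-N-SH, SH-SY5Y and SH-EP, for example by averaging them into one unit (3 vs 2 units). The analysis of seven separate lines is a sensitivity analysis. If too little is detectable, ranked effect sizes are reported and labelled exploratory. Unless independent replicate libraries exist for each line, the three-line differentiation comparison is reported descriptively, without P values. P<0.05 applies to single clinical variables.

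The sponsor should also say whether the tissue objective in 2.2.4 involves group testing. If it does, it needs a stated rule as well; the documents describe that contrast too briefly to draft one here.

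**Cost.** Wording and analysis code, with no extra samples. Software that supports moderated tests may be needed besides the Stata version named in 3.4. The main downside is a shorter, possibly empty, list: under the assumptions above, roughly 700 to 750 of 1,000 true 5-SD isoforms are found, against about 970 to 980 with seven separate lines, and only about 10 of 1,000 at 3 SD.
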